
Other secondary objectives are:
 
 
• To compare both ixekizumab regimens (80 mg Q2W or 80 mg Q4W) to placebo during the 16-week placebo-controlled period (Period 2)
 
	
 
• Proportion of patients who achieve ASAS20, ASAS40, ASAS 5/6, and partial remission by ASAS criteria
 
• Change from baseline in the individual components of the ASAS criteria
 
• Change from baseline in BASDAI
 
• Proportion of patients reaching BASDAI50
 
• Change from baseline in ASDAS
 
• Proportion of patients who experience clinically-important improvement (change of ASDAS from baseline <math>\geq 1.1</math>), major improvement (change of ASDAS from baseline <math>\geq 2.0</math>), or inactive disease (ASDAS score <math>< 1.3</math>)
 
• Change from baseline in the measure of high sensitivity C-reactive protein (CRP)
 
• Change from baseline in BASFI
 
• Change from baseline in mobility                         
 
○ Bath Ankylosing Spondylitis Metrology Index (BASMI) (linear) and individual components
 
○ Chest expansion
 
○ Change from baseline in occiput to wall distance
 
 
 
• Change from baseline in Maastricht Ankylosing Spondylitis Enthesitis Score (MASES)
 
• Change from baseline in SPARCC Enthesitis Score
 
• Change from baseline in MRI of the spine (Ankylosing Spondylitis Spinal Magnetic Resonance Imaging activity–Berlin Score [ASSpiMRI-Berlin]; this endpoint applies to MRI addendum only)
 
• Incidence and severity of peripheral arthritis by tender (TJC) and swollen joint count (SJC) scores of 46/44 joints
 
• Incidence rate of anterior uveitis or uveitis flares
 
• Change from baseline in the following health outcomes measures: Fatigue Numeric Rating Scale (NRS) score, ASAS HI score, Jenkins Sleep Evaluation Questionnaire (JSEQ), Work Productivity Activity Impairment–Spondyloarthritis (WPAI-SpA) scores, SF-36 (both PCS and mental component scores [MCS]), and Quick Inventory of Depressive Symptomatology–Self-Report (16 Items) (QIDS-SR16) score
 

Objectives	Endpoints

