### 8.4.5. *Eye Symptom Assessment*

At each study visit, study health care providers will evaluate the patient for any symptoms of anterior uveitis as specified in the Schedule of Activities ([Appendix 2](#)). If the patient has no prior ophthalmologist-diagnosed anterior uveitis and develops eye pain or discomfort, eye redness, blurring of vision, or any other symptoms suggestive of anterior uveitis, the patient must be evaluated by an ophthalmologist. If a patient has prior history of ophthalmologist-diagnosed

anterior uveitis, then she/he must be evaluated by a physician for recurrence of anterior uveitis (whenever possible, diagnosis is to be confirmed by an ophthalmologist).

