		Proportion of patients with SJC = 0 when baseline SJC > 0	SJC > 0 refers to incidence of SJC. Analysis of SJC = 0 only applies to patients whose baseline SJC > 0.	If more than half of the joint scores are nonevaluable, the total score will be missing.
		SJC change from baseline	Calculated as: observed SJC – baseline SJC	Missing if observed value is missing

Anterior Uveitis	At each study visit, study health care providers will evaluate the patient for any symptoms of anterior uveitis.	Incidence and incidence rate of anterior uveitis	Anterior uveitis will be summarized for all patients and for patients without prior anterior uveitis, separately. Anterior uveitis is identified using the preferred term “iridocyclitis.”	Missing if observed value is missing
NSAID (including COX-2 inhibitors) Intake	Information regarding NSAIDs intake will be collected in the eCRF and the ASAS-NSAID score will be calculated (Dougados et al. 2011).	Proportion of patients taking NSAID	Proportion of patients taking NSAID (including COX-2 inhibitors) at specified visit	Missing if baseline or observed value is missing
		ASAS-NSAID score	See Section 6.10.4.1 and Appendix 5 for details of deriving ASAS-NSAID score ASAS-NSAID = 0 if no NSAID use	NA
		ASAS-NSAID score change from baseline	Calculated as: observed ASAS-NSAID score – baseline ASAS-NSAID score	
		ASAS-NSAID50	$100 \times \frac{\text{Baseline ASAS} - \text{NSAID} - \text{Observed ASAS} - \text{NSAID}}{\text{Baseline ASAS} - \text{NSAID}}$ Proportion of patients with at least 50% decrease from baseline in ASAS-NSAID score. Derivation only applies to patients whose ASAS-NSAID is not equal to 0 at baseline.	
		ASAS-NSAID 10	Proportion of patients with ASAS-NSAID score <10	
		ASAS-NSAID = 0	Proportion of patients with ASAS-NSAID score = 0	

SPARCC MRI score for Spine	All 23 disco-vertebral units (DVU) of the spine (from C2 to S1) are scored for bone marrow edema. A single DVU has 18 scoring units, and each has score of 0 or 1, bringing the maximum total score to 414, with higher scores reflecting worse disease (Maksymowych et al. 2005). Scoring will be performed by central readers.	SPARCC Spine Score	The SPARCC spine score is a sum of 414 scoring units over 23 DVUs; the sum ranges from 0 to 414.	See ‘MRI Data Programming Guidance for axSpA Studies’ for missing rule and imputation method.

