Anterior Uveitis	Crude and exposure-adjusted incidence rates for patients with anterior uveitis	Fisher's exact test and Poisson regression	ITT Population	IXE80Q2W & IXE80Q4W vs. placebo during Period 2	Other secondary efficacy analyses (Section 6.10.4)
		Descriptive statistics	Extended Treatment Period Population	No treatment group comparisons during Period 3	Other secondary efficacy analyses (Section 6.10.4)
		Descriptive statistics	ITT Population Who are Initially Randomized to Ixekizumab	No treatment group comparisons during Combined Periods 2 and 3	Other secondary efficacy analyses (Section 6.10.4)
NSAID (including COX-2 inhibitors) Intake	Proportion of patients taking NSAID	Descriptive statistics	Extended Treatment Period Population	At baseline (Week 0), Weeks 16, 24, 32, 44, 52	Analyses on NSAID intake (Section 6.10.4.1)

Measure	Variable	Analysis Method (Sections 6.1, 6.3)	Population (Section 6.1.5)	Comparison/Time Point	Analysis Type
	Change from baseline in ASAS-NSAID	Descriptive statistics	Extended Treatment Period Population who have NSAID (including COX-2 inhibitor) intake at baseline	At Weeks 16, 24, 32, 44, 52	Analyses on NSAID intake (Section 6.10.4.1)
	ASAS-NSAID50; ASAS-NSAID10; ASAS-NSAID0	Descriptive statistics	Extended Treatment Period Population who have NSAID (including COX-2 inhibitors) intake at baseline	At Weeks 16, 24, 32, 44, 52	Analyses on NSAID intake (Section 6.10.4.1)

Abbreviations: ANCOVA = analysis of covariance; ASDAS = Ankylosing Spondylitis Disease Activity Score; ASAS = Assessment of Spondyloarthritis International Society; BASDAI = Bath Ankylosing Spondylitis Disease Activity Index; BASMI = Bath Ankylosing Spondylitis Metrology Index; CRP = C-reactive protein; IXE = ixekizumab; IXE80Q2W = ixekizumab 80 mg every 2 weeks; IXE80Q4W = ixekizumab 80 mg every 4 weeks; ITT = intent-to-treat; LOCF = last observation carried forward; MASES = ; mBOCF = modified baseline observation carried forward; MMRM = mixed-effects model of repeated measures; NSAID = nonsteroidal anti-inflammatory drug; NRI = nonresponder imputation; pMI = placebo multiple imputation; SJC = swollen joint count; TJC = tender joint count.

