6.12.2. Adverse Events

Adverse events will be classified based upon the latest version of the MedDRA. Adverse events will be recorded at every study visit. Any Condition starting on or after the date of informed consent will be considered an AE. Any pre-existing condition which worsens in severity on or after the date of informed consent will be considered and recorded as an AE on the *Adverse Event (AE)* eCRF page from the date of worsening onwards.

A TEAE is defined as an event that first occurred or worsened in severity after baseline and on or before the date of the last visit within the defined treatment period. Both the date/time of the event and the date/time of the dose (that is, injection) are considered when determining TEAEs. Treatment-emergent adverse events will be assigned to the study period to which it is considered treatment-emergent:

- The MedDRA Lowest Level Term (LLT) will be used when classifying AEs as treatment-emergent.
- The maximum severity recorded for each LLT before the first dose date/time in the treatment period will be used as the pretreatment severity for that LLT. If an event during the baseline period has missing severity, and the event persists during the treatment period, then it will be considered as treatment-emergent, regardless of the postbaseline level of severity. Events with a missing severity during the treatment period will be considered treatment-emergent.
- Adverse events with a particular LLT will be classified as treatment-emergent if they first start on or after the first dose date/time in the treatment period (that is, a patient has no pre-existing conditions with that LLT), or if the severity is greater than the pretreatment severity for that LLT. If a partial AE start date/time is present, the date/time will be compared as far as possible to the treatment start date/time in order to determine whether the event is treatment-emergent or not. If there is any doubt, the event will be flagged as treatment-emergent.

A follow-up emergent adverse event (FEAE) is defined as an event that first occurred or worsened in severity after the date of Visit 15 (that is, Week 52) or the ETV:

- The MedDRA LLT will be used when classifying AEs as follow-up emergent.
- For AEs that are ongoing at the date of Visit 15 or ETV, the maximum severity recorded for each LLT on or before the date of Visit 15 or ETV will be used as the follow-up baseline severity for that LLT.

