6.12.3.1. Special Safety Topics including Adverse Events of Special Interest

Safety information on special topics including AEs of special interest (AESI) will be presented by treatment group and by study period.

[Table RHBW.6.8](#) provides the definitions/derivations and analyses methods (including analyses, summaries and by-patient listings) of special safety topics including AESIs.

Potential AESIs will be identified by a Standardized MedDRA Query (SMQ) or a Lilly-defined MedDRA PT listing. Preferred Terms within an SMQ will be classified as broad and narrow. In the Lilly-defined MedDRA PT listings, Lilly has provided the broad and narrow classification. The Lilly-defined broad terms are for a more sensitive search of potential events of interest and the Lilly-defined narrow terms are for a more specific search. Therefore, the summaries will include the classifications of broad term (same as pooling narrow and broad terms together) and narrow term.

In the event that the listing of terms or analysis changes for a special safety topic, it will be documented in the program safety analysis plan (PSAP) which will supersede this document; it will not warrant an amendment to the individual study SAP.

Fisher's exact tests will be used to compare the treatment group for the safety population during Period 2.

For Period 3, summaries will be provided for the Extended Treatment Period Population.

For Combined Periods 2 and 3, selective summaries will be provided for the Safety Population which is initially randomized to ixekizumab at Week 0.

In addition, for Combined Periods 2 and 3, selective summaries will be provided for the All Ixekizumab Exposures Safety Population. In general, AESI summary will not be provided for Follow-Up Population during Period 4 except for hepatic laboratory tests.

Table RHBW.6.8. Definitions and Analyses of Special Safety Topics including Adverse Events of Special Interest

Special Safety Topic	Definition / Derivation	Analysis / Summary / Listing

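### The uveitis endpoint is counted from one preferred term, iridocyclitis, so an episode coded to any other term drops out of the endpoint

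*SAP*

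**What the plan says.** Protocol Table RHBW.1 lists among the other secondary endpoints "Incidence rate of anterior uveitis or uveitis flares". SAP Sections 4 and 6.10.4 repeat that wording.

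SAP Table RHBW.6.4 names the variable as the incidence and incidence rate of anterior uveitis. The case definition is one sentence: "Anterior uveitis is identified using the preferred term" iridocyclitis. The same cell sets the summary groups: "Anterior uveitis will be summarized for all patients and for patients without prior anterior uveitis, separately".

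SAP Table RHBW.6.5 analyses "Crude and exposure-adjusted incidence rates for patients with anterior uveitis". In Period 2 each ixekizumab regimen is compared with placebo by Fisher's exact test and Poisson regression in the ITT population. Period 3 and the combined periods are descriptive only.

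On ascertainment, Protocol Section 8.4.5 has site staff check for symptoms of anterior uveitis at each visit. A patient with no prior ophthalmologist-diagnosed episode must see an ophthalmologist. For a patient with such a history, "she/he must be evaluated by a physician for recurrence of anterior uveitis", and ophthalmologist confirmation is asked for only where possible.

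**The concern.** The endpoint is worded as a clinical entity, anterior uveitis or a flare of it. The count is a coding result. Whether an episode enters depends on the words the site writes and the preferred term they map to. No second route into the count is written down: there is no list of terms, no medical review, and no link from the eye assessment to the derived variable.

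The SAP does more for comparable topics. Section 6.12.3.1 states that "Potential AESIs will be identified by a Standardized MedDRA Query (SMQ) or a Lilly-defined MedDRA PT listing". In Table RHBW.6.8, inflammatory bowel disease has several narrow terms plus a broad list, and opportunistic infections have a term list plus medical review. No reason is given for using one term here.

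At stake is the rate for a stated endpoint with few expected events, and the Period 2 comparison built on it. Recurrences deserve particular attention because Section 8.4.5 sets a lighter confirmation requirement for them than for first episodes.

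**Working it through.** **Is there a figure to reproduce?** No. Neither document gives an event rate, power or alpha for this endpoint, and neither contains the MedDRA hierarchy. The check is therefore textual, followed by an illustration on assumed inputs.

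**Passages side by side**

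- Endpoint (Protocol Table RHBW.1; SAP 4 and 6.10.4): anterior uveitis or uveitis flares.
- Case definition (SAP Table RHBW.6.4): one preferred term, iridocyclitis.
- Coding (SAP 6.12.2): "Adverse events will be classified based upon the latest version of the MedDRA".
- Flares: not defined. Recurrences fall in the all-patient group. A count in patients with prior disease is available only as all patients minus those without prior anterior uveitis.
- Other routes to the data: SAP 6.12.2 tabulates treatment-emergent events by preferred term and lists all adverse events by patient. An episode coded to another term stays visible there but does not enter the endpoint.

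It follows that any episode not coded to iridocyclitis is excluded. Whether there are such episodes, and how many, does not follow from the text.

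**Form of the effect.** Let r be the true 16-week risk and s the share of episodes coded to iridocyclitis.

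- Reported risk = s × r, so the shortfall is 1 − s: 10% at s = 0.9, 25% at s = 0.75, 50% at s = 0.5.
- Ratio between arms with the same s in both: (s × r₁)/(s × r₀) = r₁/r₀, unchanged. The absolute difference shrinks to s × (r₁ − r₀).
- Chance that an arm of 100 shows no counted event: (1 − s × r)¹⁰⁰.

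**Illustration** (r and s are both assumptions; 100 per arm is the planned group size):

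| r | s | expected counted cases | chance of counting none |
|---|---|---|---|
| 2% | 1 | 2.0 | 13.3% |
| 2% | 0.5 | 1.0 | 36.6% |
| 3% | 1 | 3.0 | 4.8% |
| 3% | 0.9 | 2.7 | 6.5% |
| 3% | 0.75 | 2.25 | 10.3% |
| 3% | 0.5 | 1.5 | 22.1% |
| 5% | 1 | 5.0 | 0.6% |
| 5% | 0.5 | 2.5 | 8.0% |

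**Effect on the Period 2 test.** Two-sided Fisher p-values for one arm against another, 100 each: 3 v 0, p = 0.25; 5 v 0, p = 0.06; 6 v 0, p = 0.03; 5 v 1, p = 0.21; 7 v 1, p = 0.06. At counts this small, one or two added cases would seldom move a result across 0.05. If the true risks were 5% and 1%, power would be 19.4% with full capture and 9.5% at s = 0.75 (3.75% v 0.75%). The test is weak either way. The rates themselves are what the definition mainly affects.

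**The case against.** The case for leaving the plan alone has real weight.

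- **The coding step is unseen.** An episode is lost only if the reported words map outside iridocyclitis, and the dictionary is in neither document. This stands: it is an assumption, and the sponsor can settle it by looking.
- **Flares are not dropped.** A reader might infer that the second half of the endpoint is ignored. The text does not support that. Recurrences coded to iridocyclitis are in the all-patient count and can be obtained by subtraction. The documents also treat a flare as a recurrence of anterior uveitis: Protocol Appendix 5 defines the uveitis feature as anterior, and Section 8.4.5 speaks of "she/he must be evaluated by a physician for recurrence of anterior uveitis".
- **Ascertainment favours a specific label.** Symptoms are sought at each visit, and suspected episodes go to an ophthalmologist or physician. This lowers the likely loss but does not remove it, because nothing links the eye evaluation to the count. Equally, nothing in the documents shows that flares are the reports most likely to be worded loosely.
- **Nothing is lost from the record.** True, but the adverse event tables are not this endpoint or its tests.
- **One term is specific.** A broad list may admit non-anterior disease, so a narrow definition is defensible. That argues for keeping it as one of two definitions. It does not argue against showing the other.
- **Low consequence.** The endpoint is outside the multiplicity procedure, and the later-period analyses are descriptive. This stands and limits the priority.

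**Conclusion.** The point holds as a gap in the case definition. One preferred term defines the endpoint, so any episode coded to another term is left out of it, although still reported elsewhere. That episodes will in fact be lost rests on one assumption: that words such as uveitis or iritis code to terms of their own in the MedDRA version used.

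Two stronger readings are not supported. A reader might put a percentage on the understatement, but any such figure only restates an assumed share s. The documents give neither s nor an event rate. A reader might also infer that the comparison with placebo is biased. In a double-blind trial nothing suggests that wording or coding differs by arm. With a common s, the rates are low in every arm and precision falls, while the ratio need not be biased.

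No primary or major secondary conclusion is touched. This is a low-cost improvement to an other secondary endpoint.

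**What to change.** 1. Check in the MedDRA version used which reported words map to iridocyclitis and which do not.
2. In SAP Table RHBW.6.4, prespecify a broad definition: iridocyclitis plus uveitis, iritis and other anterior-segment uveitis terms. Report it beside the iridocyclitis-only count, kept as the narrow definition.
3. Have the existing sponsor medical staff check any unspecified-uveitis case against the eye evaluation, masked to treatment where blinding still holds.
4. Show patients with prior anterior uveitis as their own row, so that flares are visible without subtraction.
5. Label the broad count supplementary for the Week 16 data. The SAP revision history places Version 3 (June 2018) before first unblinding and Version 4 (February 2019) before the Week 52 lock, so a change made now follows the Week 16 unblinding.

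The cost is a short term list, one extra row or column in the tables, and review of what should be few cases. The drawback is that the broad list may include an occasional non-anterior case. The review in step 3 should catch most of these, and the narrow count remains alongside.

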6.1.5. Analysis Populations

The following major analysis populations will be used (additional analysis populations for specific analysis will be defined in the corresponding analysis section):

Intent-to-Treat Population (ITT Population): Unless otherwise specified, efficacy and health outcomes analyses for Period 2 will be conducted on the ITT Population, defined as all randomized patients, even if the patient does not take the assigned treatment, does not receive the correct treatment, or otherwise does not follow the protocol. Patients will be analyzed according to the treatment to which they were assigned.

Per-Protocol Set (PPS): In addition, the primary efficacy analysis will be repeated using the PPS, which is defined as all randomized patients who do not have a subset of important protocol deviations that impact the primary efficacy endpoint (Section 6.14). For example, patients who are not compliant with therapy during the double-blind period will be excluded from the PPS. Compliance with therapy is defined to be missing no more than 20% of expected doses, not missing 2 consecutive doses (all injections in an injection week are counted as 1 dose), and not have any occurrence of over-dosing (that is, took more injections at the same time point than specified in the protocol) during Period 2.

Patients will be analyzed according to the treatment to which they were assigned.

Safety Population: Safety analyses for Period 2 will be conducted on the Safety Population, defined as all randomized patients who received at least 1 dose of study treatment. Patients will be analyzed according to the treatment to which they were assigned in that period.

Extended Treatment Period Population: Efficacy, health outcomes, and safety analyses for Period 3 will be conducted on the Extended Treatment Period Population, defined as all patients who received at least 1 dose of ixekizumab treatment during Period 3.

All Ixekizumab Exposures Safety Population: Safety analyses for combined Blinded Treatment Dosing Period and Extended Treatment Period will be conducted on the All Ixekizumab Exposures Safety Population, defined as all patients who received at least 1 dose of ixekizumab during the study. For each patient, only periods in which ixekizumab is administered are included.

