		SPARCC enthesitis score = 0	SPARCC enthesitis score = 0 refers to complete resolution in enthesitis Analysis of SPARCC enthesitis score = 0 only applies to patients with baseline enthesitis (SPARCC enthesitis >0).	Missing if >20% (ie, 4 or more) sites are missing. If ≤20% missing, then imputed sum = sum of scores from nonmissing sites x 16/ no. of nonmissing sites.

Description and Derivation of Primary and Secondary Efficacy Outcomes

Tender Joint Count (TJC)	The number of tender and painful joints will be determined by examination of 46 joints (23 joints on each side of the patient’s body). The 46 joints are assessed and classified as tender or not tender.	TJC total score	Adjusted sum of the pain/tenderness for all 46 joints: $\left(\frac{\text{sum of all joints checked to be painful/tender}}{\text{number of evaluable joints}}\right) \times 46$ See Appendix 4 for details.	Missing if baseline or observed value is missing
		Proportion of patients with TJC = 0 when baseline TJC > 0	TJC > 0 refers to incidence of TJC. Analysis of TJC = 0 only applies to patients whose baseline TJC > 0.	Missing if observed value is missing
		Proportion of patients with TJC = 0 for patients with current or historical peripheral arthritis at baseline	TJC > 0 refers to incidence of TJC. Analysis of TJC = 0 only applies to patients with current or historical peripheral arthritis at baseline.	If more than half of the joint scores are non-evaluable, the total score will be missing.
		TJC change from baseline	Calculated as: observed TJC – baseline TJC only applies to patients whose baseline TJC > 0.	Missing if observed value is missing
Swollen Joint Count (SJC)	The number of swollen joints will be determined by examination of 44 joints (22 joints on each side of the patient’s body). The 44 joints are assessed and classified as swollen or not swollen.	SJC total score	Adjusted sum of the pain/tenderness for all 44 joints: $\left(\frac{\text{sum of all joints checked to be swollen}}{\text{number of evaluable joints}}\right) \times 44$ See Appendix 4 for details.	Missing if observed value is missing

Description and Derivation of Primary and Secondary Efficacy Outcomes

		Proportion of patients with SJC = 0 for patients with current or historical peripheral arthritis at baseline	SJC > 0 refers to incidence of SJC. Analysis of SJC = 0 only applies to patients with current or historical peripheral arthritis at baseline.	Missing if baseline or observed value is missing

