CRP	CRP change from baseline; ratio of postbaseline to baseline CRP	MMRM	ITT Population	IXE80Q2W & IXE80Q4W vs. placebo at Week 16 and all other postbaseline visits in Period 2	Other secondary efficacy analyses (Section 6.10.4)
		ANCOVA with mBOCF	ITT Population	IXE80Q2W & IXE80Q4W vs. placebo at Week 16 and all other postbaseline visits in Period 2	Other secondary efficacy analyses (Section 6.10.4)
		MMRM	ITT Population	IXE80Q2W & IXE80Q4W Starting Dose 160 mg and 80 mg during Period 2	Other secondary efficacy analyses (Section 6.10.4)
		Descriptive statistics of change from baseline	Extended Treatment Period Population	No treatment group comparisons during Period 3	Other secondary efficacy analyses (Section 6.10.4)

Measure	Variable	Analysis Method (Sections 6.1, 6.3)	Population (Section 6.1.5)	Comparison/Time Point	Analysis Type
Mobility-Related Measures	BASMI linear (incl. 5 components); chest expansion, occiput to wall distance change from baseline	MMRM	ITT Population	IXE80Q2W & IXE80Q4W vs. placebo at Week 16 and all other postbaseline visits in Period 2	Other secondary efficacy analyses (Section 6.10.4)
		ANCOVA with mBOCF	ITT Population	IXE80Q2W & IXE80Q4W vs. placebo at Week 16 and all other postbaseline visits in Period 2	Other secondary efficacy analyses (Section 6.10.4)
		Descriptive statistics of change from baseline	Extended Treatment Period Population	No treatment group comparisons during Period 3	Other secondary efficacy analyses (Section 6.10.4)
Enthesitis Scores	MASES and SPARCC change from baseline	MMRM	ITT Population with Baseline MASES >0(or SPARCC >0)	IXE80Q2W & IXE80Q4W vs. placebo at Week 16 and all other postbaseline visits in Period 2	Other secondary efficacy analyses (Section 6.10.4)
		ANCOVA with mBOCF	ITT Population with Baseline MASES >0(or SPARCC >0)	IXE80Q2W & IXE80Q4W vs. placebo at Week 16 and all other postbaseline visits in Period 2	Other secondary efficacy analyses (Section 6.10.4)
		Descriptive statistics of change from baseline	Extended Treatment Period Population with Baseline MASES >0(or SPARCC >0)	No treatment group comparisons during Period 3	Other secondary efficacy analyses (Section 6.10.4)
	MASES score = 0 (similarly SPARCC = 0)	Logistic regression analysis with NRI; Fisher's exact test with NRI	ITT Population with Baseline MASES >0(or SPARCC >0)	IXE80Q2W & IXE80Q4W vs. placebo at Week 16 and all other postbaseline visits in Period 2	Other secondary efficacy analyses (Section 6.10.4)

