Measure	Variable	Analysis Method (Sections 6.1, 6.3)	Population (Section 6.1.5)	Comparison/Time Point	Analysis Type
		Descriptive statistics of MASES = 0 (or SPARCC=0)	Extended Treatment Period Population with Baseline MASES >0 (or SPARCC >0)	No treatment group comparisons during Period 3	Other secondary efficacy analyses (Section 6.10.4)
Peripheral Arthritis	TJC and SJC change from baseline	MMRM	ITT Population with Baseline TJC>0 (or SJC>0)	IXE80Q2W & IXE80Q4W vs. placebo at Week 16 and all other postbaseline visits in Period 2	Other secondary efficacy analyses (Section 6.10.4)
		ANCOVA with mBOCF	ITT Population with Baseline TJC>0 (or SJC>0)	IXE80Q2W & IXE80Q4W vs. placebo at Week 16 and all other postbaseline visits in Period 2	Other secondary efficacy analyses (Section 6.10.4)
		Descriptive statistics of change from baseline	Extended Treatment Period Population	No treatment group comparisons during Period 3	Other secondary efficacy analyses (Section 6.10.4)
	TJC = 0, SJC=0, respectively, when patients had current or historical peripheral arthritis at baseline	Logistic regression analysis with NRI; Fisher’s exact test with NRI	ITT Population with current or historical peripheral arthritis at baseline	IXE80Q2W & IXE80Q4W vs. placebo at Week 16 and all other postbaseline visits in Period 2	Other secondary efficacy analyses (Section 6.10.4)
		Descriptive statistics of TJC = 0 (or SJC =0)	Extended Treatment Period Population with current or	No treatment group comparisons during Period 3	Other secondary efficacy analyses (Section 6.10.4)

Measure	Variable	Analysis Method (Sections 6.1, 6.3)	Population (Section 6.1.5)	Comparison/Time Point	Analysis Type
			historical peripheral arthritis at baseline		
	TJC = 0 when baseline TJC >0 (similarly SJC = 0 when baseline SJC >0)	Logistic regression analysis with NRI; Fisher's exact test with NRI	ITT Population with Baseline TJC>0 (or SJC>0)	IXE80Q2W & IXE80Q4W vs. placebo at Week 16 and all other postbaseline visits in Period 2	Other secondary efficacy analyses (Section 6.10.4)
		Descriptive statistics of TJC = 0 (or SJC =0)	Extended Treatment Period Population with Baseline TJC>0 (or SJC>0)	No treatment group comparisons during Period 3	Other secondary efficacy analyses (Section 6.10.4)

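### The Period 3 joint-count change summary drops the baseline >0 limit used in Period 2, so mean SJC change is not comparable with Week 16, and for TJC two SAP tables conflict

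*SAP*

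**What the plan says.** SAP Table RHBW.6.5 (Section 6.10), under Peripheral Arthritis, lists three analyses of "TJC and SJC change from baseline". The two Period 2 analyses, MMRM and ANCOVA with mBOCF, use the "ITT Population with Baseline TJC>0 (or SJC>0"). The Period 3 analysis, descriptive statistics of change, uses the "Extended Treatment Period Population" with no condition on baseline count. Section 6.1.5 gives that population as "defined as all patients who received at least 1 dose of ixekizumab treatment during Period 3".

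Table RHBW.6.4, which derives the variables, treats the two counts differently. For TJC change it says: "Calculated as: observed TJC – baseline TJC only applies to patients whose baseline TJC > 0". No period is named. For SJC change it says only: "Calculated as: observed SJC – baseline SJC".

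Neighbouring Period 3 rows of Table RHBW.6.5 keep a baseline limit. Enthesitis change uses the "Extended Treatment Period Population with Baseline MASES >0(or SPARCC >0"). One pair of TJC = 0 and SJC = 0 rows uses the "Extended Treatment Period Population with Baseline TJC>0 (or SJC>0"), and another uses patients with current or historical peripheral arthritis at baseline.

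SAP Section 4 lists maintenance of effect through Week 52 as an other secondary objective and carries the Period 2 endpoints forward to Week 52, apart from MRI. SAP Section 6.10.4 makes Period 3 descriptive, with no inferential testing.

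**The concern.** Someone asking whether the joint-count effect lasts would set the Week 16 mean change beside the Week 52 mean change. As planned, the Week 16 figure comes from patients with affected joints at baseline. The Week 52 SJC figure comes from everyone dosed in Period 3, including patients who started at zero and have no room to improve. A fully maintained effect could then look like a partial loss.

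No other planned table of mean change closes the gap. The Combined Periods 2 and 3 efficacy analyses in SAP Section 6.1.3 cover the primary and major secondary endpoints, BASDAI50 and certain ASDAS categories, but not joint counts. Week 16 is measured before the injection that opens Period 3 (Sections 6.1.1 and 6.1.2). The protocol's Schedule of Activities then has joint counts at Weeks 24, 36 and 52. So the plan does not call for a Week 16 mean change on the Period 3 basis.

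For TJC the difficulty is different: a programmer meets a derivation that restricts the variable and a population cell that does not, and must choose.

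**Working it through.** The documents state no figure for joint counts, so there is none to reproduce. The check is a comparison of the table cells followed by mixture arithmetic.

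**1. Population by row (SAP Tables RHBW.6.4 and RHBW.6.5)**

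| Variable | Period 2 population | Period 3 population | Limit in Table RHBW.6.4 |
|---|---|---|---|
| TJC change | baseline TJC >0 | no limit | baseline TJC >0 |
| SJC change | baseline SJC >0 | no limit | none |
| TJC = 0, SJC = 0 | baseline count >0 | baseline count >0 | baseline count >0 |
| MASES, SPARCC enthesitis change | baseline score >0 | baseline score >0 | none |

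Joint-count change is the only one of these whose limit in Table RHBW.6.5 disappears between periods. For TJC the derivation still carries it. For SJC nothing does. The enthesitis derivations have no limit either, but there Table RHBW.6.5 supplies it in both periods.

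**2. Effect on the mean**

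Let f be the share of a Period 3 treatment group with baseline SJC >0, D the mean change in those patients, and m0 the mean change in patients with baseline SJC = 0. Because a zero count cannot fall, m0 is at least 0. Then

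mean(all) = f × D + (1 − f) × m0.

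SAP Section 6.7.1 plans to report the number and percentage with any swollen joint at baseline but gives no expected value, so f, D and m0 are all assumptions. Take D = −4, identical at Week 16 and Week 52 (full maintenance):

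| f | m0 = 0 | Share of D | m0 = 0.5 | Share of D |
|---|---|---|---|---|
| 0.3 | 0.3 × (−4) = −1.20 | 30% | −1.20 + 0.7 × 0.5 = −0.85 | 21% |
| 0.5 | 0.5 × (−4) = −2.00 | 50% | −2.00 + 0.5 × 0.5 = −1.75 | 44% |
| 0.8 | 0.8 × (−4) = −3.20 | 80% | −3.20 + 0.2 × 0.5 = −3.10 | 78% |

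With m0 = 0 the share is f itself, whatever D is. With m0 above 0 it is smaller. With the limit restored, the Period 3 mean is D at every f.

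**3. Effect on the median**

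Section 6.1.2 also reports the median. If f is below 0.5, fewer than half the patients can have a negative change, so the median SJC change is 0 or higher however well the affected patients do.

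**The case against.** The strongest reply has four parts.

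- **TJC.** The derivation limits TJC change to baseline TJC above zero without naming a period, so the Period 3 row can be read as that restricted variable summarised in the Period 3 population. This stands. A reader of Table RHBW.6.5 alone might infer that both joint counts are diluted, but the documents do not support that. For TJC the fault is disagreement between two tables.
- **Maintenance.** A reader might go further and infer that the plan cannot show maintenance of the joint-count effect. It can, in part. The TJC = 0 and SJC = 0 summaries use the same baseline criterion in both periods, and even an unrestricted SJC series can show a trend over Weeks 24, 36 and 52. This stands, although those summaries give complete resolution, not size of change.
- **Other differences between periods.** Period 2 gives model-based estimates in ITT patients. Period 3 gives raw mBOCF summaries in patients dosed in Period 3. The reported n and the baseline percentages with affected joints would also reveal the changed denominator. This is true, but seeing a different n does not let a reader recover D, and the other differences do not remove this one.
- **A possible reason for the wider population.** The endpoint covers incidence as well as severity of peripheral arthritis, and patients starting at zero can develop swollen joints. The SAP gives no such reason. The retained limits in adjacent rows, and a Version 2 change entry that updates the enthesitis and joint-count populations together, suggest an omission. The documents do not settle it.

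**Conclusion.** The point holds for mean change. For SJC, following the SAP as written gives Period 3 means that are pulled toward zero and are not comparable with the Week 16 analysis. The unrestricted mean is at most the fraction f of the change in affected patients, and less if patients starting at zero acquire swollen joints. The size rests entirely on f, which the documents do not give: an apparent loss of 70% at f = 0.3, 50% at 0.5 and 20% at 0.8 under full maintenance (1 − f with m0 = 0). For TJC, Tables RHBW.6.4 and RHBW.6.5 must be reconciled; dilution follows only if the population cell overrides the derivation.

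The consequence is small. This is an other-secondary, descriptive summary outside the multiplicity procedure of SAP Section 6.5, and no primary or major secondary result depends on it. It is worth correcting because the correction is nearly free.

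**What to change.** - In Table RHBW.6.5, change the population of the Period 3 joint-count change row to the wording already used for the Period 3 TJC = 0 and SJC = 0 rows: "Extended Treatment Period Population with Baseline TJC>0 (or SJC>0"), with each count limited by its own baseline.
- In Table RHBW.6.4, add a baseline SJC >0 limit to the SJC change row, matching the TJC row.
- Show the Week 16 mean change in that same Period 3 subset beside Weeks 24, 36 and 52, so that one fixed group is followed across the transition.

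The cost is two table cells and one extra visit in a descriptive output, with no new data. There is one small downside: new swollen joints in patients with baseline SJC = 0 would no longer enter the mean change. The Period 3 SJC = 0 summary in patients with current or historical peripheral arthritis would pick up some of them.
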